6.1 Population Characteristics

6.1.1 Disposition of Patients

The number and percent of patients included in the FAS will be summarized for both the larotrectinib and external cohorts.

6.1.2 Demographic and Baseline Characteristics

Descriptive summaries of demographics and baseline characteristics will be presented for each cohort and overall. The following baseline data will be summarized:

- Patients and disease characteristics:
 - Sex,
 - Age,
 - Disease history:
 - Locally Advanced or Metastatic Disease
 - Primary Tumor Location
 - Time from initial diagnosis to first dose of larotrectinib (SCOUT) or first line of chemotherapy (external cohorts),
 - Time from locally advanced/metastatic disease diagnosis to initiation of larotrectinib (SCOUT) or first line of chemotherapy (external cohorts),
 - The resectability (Intergroup Rhabdomyosarcoma Study) IRS classification stage
- Collection of treatment-related information:
 - Prior surgical treatment(s) for cancer:
 - Number of previous surgical resections
 - Amputated leg (yes/no)
 - Amputated arm (yes/no)
 - Other surgical intervention (categorization to be decided after medical review)
 - Prior radiation treatment(s) for cancer:
 - Prior radiotherapy (yes/no)
 - Duration of most recent radiotherapy
 - Anatomical sites
 - Start / stop dates (listing only).
 - Systemic treatment(s):
 - Number of prior systemic regimens, and categorization of treatment regimens
 - Reasons for discontinuation
 - Start / stop dates (listing only)
 - Best response to last systemic treatment (complete response (CR), partial response (PR), SD, PD, NE). Note: NE is defined as not evaluable / not done.
 - Number of cycles

6.1.3 Systematic Literature Review

A SLR was conducted in order to identify and quantify the impact of prognostic factors on the primary endpoint. The report found that there was a lack of evidence in the literature on prognostic factors that might have an influence on clinical outcomes for patients with IFS.

The SLR identified only 5 studies, and due to the rarity of the disease all studies had a small sample size leading to a high degree of imprecision in the results. The report has highlighted the following core subset of prognostic factors for inclusion into the PS model.

6.1.4 Core subset of prognostic variables

IRS initial resectability classification

IRS group was the most studied prognostic factor in the literature in terms of its impact on overall survival (OS). IRS Stage has 4 groups, but most of the studies (Orbach 2010, Cecchetto 2001, Sulkowski 2013) compared the impact of IRS I *versus* IRS II or IRS I *versus* IRS II/III on clinical outcomes. Those studies suggested that IRS I may be an indicator of better prognosis, either in terms of OS or event-free survival (EFS), than IRS II or III. No studies investigated the impact of IRS IV (which corresponds to metastatic disease stage) on clinical outcomes compared to other IRS groups.

The IRS initial resectability classification was not collected in SCOUT study, however given it is reported as a prognosis factor in the literature, in order to allow to feature it in the PS model, IRS for SCOUT IFS patients will be derived from their disease status. Locally advanced disease corresponds as per medical expert opinion (PI. [name]) to IRS III and metastatic disease to IRS IV (as per IRS definition).

Locally advanced *versus* metastatic disease stage

We have no knowledge of locally advanced *versus* metastatic disease stage being studied on clinical outcomes due to a lack of metastatic patients included in any IFS studies. However, the broad expert consensus is that metastatic disease stage is likely to have a significant effect on endpoints in comparison to locally advanced patients. Given IRS initial resectability classification already captures the stage of the disease, the impact of disease stage will be already accounted for and an additional variable locally advanced vs metastatic disease stage is not needed to feature in the PS model.

Primary Tumor Localization

Two studies explored the impact of primary tumor localization (axis *versus* extremity) on clinical outcomes (Orbach 2010[11], Cecchetto 2001). Only Orbach 2010 explored its impact on EFS, which did not reveal a statistical difference between tumor locations. Both studies found consistent results that tumor localization did not have an impact on OS. However, the Cecchetto study did include both infantile and adult fibrosarcoma patients, and results from this study may not be fully representative of the current study. Therefore, tumor location will not form part of the core prognostic factors for the PS model.

Tumor Size

Two studies explored the impact of tumor size on clinical outcomes (Orbach 2010, Sparber Sauer 2020). Both studies concluded that tumor size (≤ 5 cm, > 5 cm) did not have an impact on EFS. Furthermore, the Orbach [2010] study did not find tumor size to be a prognostic factor of OS. As tumor size factors into IRS group stage (IRSG), tumor size will only contribute indirectly to the propensity score through IRSG.

Age

The SLR did not uncover any evidence of age having a statistically significant prognostic value on EFS and OS, probably due to small sample sizes. However, age will be retained as a prognostic factor due to the clinical importance of the covariate.

Time from locally advanced/metastatic disease diagnosis to initiation of larotrectinib (SCOUT) or first line of chemotherapy (external cohorts)

Based on the SLR, no study investigated how time from diagnosis to initiation of therapy affects clinical outcomes. Time from locally advanced/metastatic disease to initiation of treatment will be added to the core subset, acknowledging that there will likely be an initial imbalance on lines of therapy between treatment groups. Line of therapy will be substituted by elapsed time from locally advanced/metastatic disease in the PS model.

6.2 Analysis of Primary Variable(s)

6.2.1 Primary Endpoint

The primary endpoint of the study is the time to medical treatment failure: defined as the time (months) from the start of treatment to the date of the earliest event from: subsequent systemic treatment, radiation therapy, mutilating surgery or death due to any cause.

The **index** date of the analysis of the primary endpoint will be defined as either the start date of larotrectinib treatment (for patients in the SCOUT study, regardless of line of therapy) or start date of chemotherapy (first line) for the external historical control cohorts. The end date is defined as the earliest of the following endpoints:

- Start date of a post-treatment systemic anti-cancer therapy, if any, or,
- Start date of a post-treatment radiation therapy, if any, or,
- Date of a post-treatment mutilating surgery, if any, or,
- Date of death due to any cause, if applicable.

Patients who do not record an event will be censored at the last known alive date.

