	
For the OS endpoint:
 
 • Start date of larotrectinib treatment for the SCOUT study and start date of chemotherapy (first line) for the external historical control cohort(s), and, • Date of death due to any cause, if applicable, or, • Last date of patient follow-up for patients alive and lost to follow-up, if applicable. 
For the Incidence of patients with treatment discontinuation due to treatment-related AEs endpoint:
 
 • Record of treatment⁴ discontinuation due to treatment-related AEs, if applicable. 
Variables to determine the exploratory endpoints:
 
For the PFS endpoint:
 
 • Start date of larotrectinib treatment for the SCOUT study and start date of chemotherapy (first line) for locally-advanced/metastatic disease for the external historical control cohort(s), and, • Date of first post-treatment⁵ disease progression/relapse assessed by radiological or clinical examination by investigator, if any, or, • Date of death due to any cause, if applicable, or, • Censored at last date of tumor assessment. A complete list of censoring rules will be provided in the statistical analysis plan (SAP). 
For the ORR and DCR endpoints:
 
 • Patient response to treatment⁴ (CR, PR and SD) assessed by investigator. 
Potential confounders:
 
The following baseline variables will be considered when balancing the two cohorts: patients with IFS enrolled in SCOUT and the external historical control cohort(s).
 
 • Patients and disease characteristics: 
 ○ Sex, ○ Age, ○ Disease history: 
 ■ Date of initial diagnosis,
--	---

⁴ Larotrectinib treatment for the SCOUT study and chemotherapy (first line) for the external historical control cohort(s).

⁵ After the start of larotrectinib treatment for the SCOUT study or after the start of chemotherapy (first line) for the external historical control cohort(s).

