9.3.4 Potential confounders

The following baseline variables will be considered when balancing the two cohorts: IFS patients enrolled in SCOUT study and the external historical control cohort(s).

- Patients and disease characteristics:
 - Sex,
 - Age,
 - Disease history:
 - Date of initial diagnosis,
 - Anatomical disease site(s) at diagnosis,
 - Stage of disease at diagnosis (local versus locally advanced versus metastatic),
 - Primary tumor size (< 5 cm or > 5 cm),
 - Date of advanced disease stage evolution (locally advanced, metastatic),
 - Time from locally advanced/metastatic disease diagnostic to initiation of larotrectinib (SCOUT) or first line of chemotherapy (external historical control cohort(s)),
 - Intergroup Rhabdomyosarcoma Study (IRS) group,
 - Anatomical site(s) of metastases, if any.
- Collection of treatment-related information:
 - Prior/current surgical treatment(s) for cancer:
 - Anatomical site(s),

⁹ Larotrectinib treatment for the SCOUT study and chemotherapy (first line) for the external historical control cohort(s).

- Date(s) of surgery,
- Best resection (R0, R1, R2),
- Nature of intervention(s) (e.g. amputation or other disfiguring procedures),
- Surgery for a curative intent (excluding amputation) because of the use of systemic treatment.
- Prior/current radiation treatment(s) for cancer:
 - Anatomical sites,
 - Date(s) of radiation therapy.
- Systemic treatment(s), including:
 - Treatment regimen,
 - Date of initiation,
 - Date of radiological or clinical progression,
 - Reasons for discontinuation, as appropriate.

A SLR will be conducted to identify and quantify prognostic factors which could impact the study primary endpoint. This SLR is based on a protocol of research including the following PICO criteria:

- Population: IFS locally advanced or metastatic.
- Intervention: no restriction.
- Comparison: no restriction.
- Outcomes: prognostic factors.
- Type of studies: no restriction except case reports.
- Period: no limit of time.
- Scope: international.

The SLR protocol and report will be annexed to the final study report.

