9.7.1 Index Date and endpoints

The comparison of the two cohorts will be considered for the primary composite endpoint:

- Time-to-treatment-failure (earliest of next systemic therapy, radiotherapy, mutilating surgery or death due to any cause).

In addition, all secondary and exploratory endpoints detailed in [Section 9.1.2](#) and [Section 9.1.3](#) will be analyzed:

- Time to subsequent systemic treatment,
- Time to mutilating surgery or limb amputation,
- Time to radiation therapy,
- Time to complete surgical resection (excluding amputation),
- OS,
- PFS,
- Incidence of treatment discontinuation due to treatment-related AEs,
- ORR,
- DCR.

The analysis will include patients on both first and second line (or higher) therapy. For SCOUT patients, the index date will be defined as the start date of larotrectinib. For patients of the external historical control cohort(s), the index date will be the start date of the first line of chemotherapy. The initial imbalance on lines of therapy between treatment groups will be corrected in the statistical modeling, in particular the variable defined by time from locally advanced/metastatic disease to index date will be a key variable in the propensity score model. Given approximately 70% of SCOUT patients received larotrectinib as second line of treatment, while in the external historical control cohort(s) all patients will have received chemotherapy in first line of treatment, the proposed primary analysis is expected to provide a rather conservative estimate of treatment effect.

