5.1 Assignment of Analysis Sets

FAS

A patient will be included in the FAS if the patient has taken at least one dose of larotrectinib for SCOUT study, or has fulfilled the eligibility criteria for inclusion into the pooled external cohorts and has initiated chemotherapy.

All analyses detailed below will be repeated separately for two populations of FAS:

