5.1.1 IFS Population

- Age \leq 21 years old
- Locally advanced or metastatic IFS
- Patients receiving
 - larotrectinib in the SCOUT trial, or
 - receiving at least one chemotherapy-based regimen in the external historical control cohorts.

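### Control eligibility has no time anchor and the control index date has no stage condition, so a control could qualify through an event that happens after its own index date

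*SAP*

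**What the plan says.** **Index date.** Protocol 9.7.1 says that for controls "the index date will be the start date of the first line of chemotherapy". Protocol 9.3.1 and SAP 6.2.1 use the same rule; the SAP wording is "or start date of chemotherapy (first line) for the external historical control cohorts". None of these places mentions stage. SCOUT patients are indexed at the start of larotrectinib.

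**Eligibility.** Protocol 9.2.3.2 and SAP 5.1.1 require "Locally advanced or metastatic IFS" without saying when this must be true. SAP 5.1 admits a control who "has fulfilled the eligibility criteria for inclusion into the pooled external cohorts and has initiated chemotherapy", which sets no order between the two conditions.

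**Change of stage over time.** Protocol 9.3.4 lists "Stage of disease at diagnosis (local versus locally advanced versus metastatic" and, as a separate item, "Date of advanced disease stage evolution (locally advanced, metastatic". The plan therefore allows for patients who are local at diagnosis and advance later.

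**The one place that ties the control start to stage.** In the Protocol abstract (Section 4), the PFS variables use "start date of chemotherapy (first line) for locally-advanced/metastatic disease for the external historical control cohort(s". The PFS text in Protocol 9.3.3 and SAP 6.3.6 omits that condition, as does every statement of the primary endpoint.

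**The concern.** In an externally controlled comparison, a patient should meet the entry criteria at time zero, using only what was known by then. Here a control can meet the stage criterion after time zero.

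Take two patients given first-line chemotherapy for local disease. One later develops metastases and starts a second regimen. That patient now has metastatic disease, satisfies SAP 5.1.1, is indexed at the earlier chemotherapy, and has a primary endpoint event when the second regimen starts. The other never advances and is never eligible. The first enters because of what happened after index, and the favourable counterpart is left out.

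SCOUT has no matching route, because its clock starts at larotrectinib in a trial of advanced tumours. The effect would tend to raise the control failure rate. Protocol 9.7.1 and SAP 6.2.5 describe the primary analysis as leaning, if anything, against larotrectinib, and they do not consider a mechanism that runs the other way. With so few events expected, a handful of such controls would be visible in the result.

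**Working it through.** **1. The plan's own figure.** SAP Section 4 gives 49 SCOUT patients, 42 controls, pE = 0.04, pC = 0.19 and HR = 0.25. Then k = 49/42 = 1.167 and m = 49 × 0.04 + 42 × 0.19 = 9.94. Power = Φ(√(km)·|HR − 1|/(k·HR + 1) − 1.96) = Φ(3.405 × 0.75/1.292 − 1.96) = 50.7%, against the stated 51%. The inputs are therefore read correctly. Power does not test this point, which concerns who enters the control arm.

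**2. Do the rules close the gap?**

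| Place | Stage required on or before control index? |
|---|---|
| Protocol 9.2.3.2, SAP 5.1.1 (eligibility) | No date given |
| SAP 5.1 (FAS) | No order given |
| Protocol 9.3.1, 9.7.1; SAP 6.2.1 (primary index) | No stage given |
| Protocol abstract, PFS variables | Yes, for PFS only |
| Protocol 9.3.3, SAP 6.3.6 (PFS) | No |
| SAP 6.1.2, 6.1.4 (time from advanced disease to index) | Presumed, not required; no rule for a negative value |

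**3. Expected control failures.** 42 × 0.19 = 7.98, about 8. Separately, Table 2 in SAP Section 7 shows 8 of 42 controls (19%) at second line or higher, and a second line after first-line index is itself a primary event.

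**4. Illustration.** The number of affected controls is not in the documents; 2 and 4 of the 8 failures are assumptions. A control with a later chemotherapy line would be re-indexed and kept, and may or may not fail again. A control with no such line would be removed.

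| Affected | All re-indexed and kept (none to all fail again) | All removed |
|---|---|---|
| 0 | 8/42 = 19.0% | 8/42 = 19.0% |
| 2 | 6/42 = 14.3% to 8/42 = 19.0% | 6/40 = 15.0% |
| 4 | 4/42 = 9.5% to 8/42 = 19.0% | 4/38 = 10.5% |

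**5. Direction under no true difference.** Suppose both arms fail at 0.19, but j of the 42 controls are certain failures. The apparent control rate is (j + (42 − j) × 0.19)/42, and under proportional hazards the apparent HR is ln(1 − 0.19)/ln(1 − that rate).

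- j = 2: (2 + 7.6)/42 = 0.229, apparent HR 0.81.
- j = 4: (4 + 7.22)/42 = 0.267, apparent HR 0.68.

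Both lie below 1, in favour of larotrectinib.

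**The case against.** The best reply is that chemotherapy for advanced disease was plainly meant. The abstract's PFS wording says so. The core propensity covariate, "Time from locally advanced/metastatic disease diagnosis to initiation of larotrectinib (SCOUT) or first line of chemotherapy (external cohorts", makes sense only if advanced disease comes first. SAP 4.5 takes control baseline values on or before first-line chemotherapy, and SAP 6.1.2 lists advanced stage as a baseline characteristic with no local category. SAP Section 4 sends eligibility questions to a Data Management Plan, which may settle the timing. The background sections also make the case look uncommon: chemotherapy is described mainly for tumours that cannot be resected upfront, and a patient resected first who has chemotherapy only after advancing is indexed correctly. Finally, the second-line subgroup and the second-line stratum of the exact matching in SAP 6.2.5 start controls at the later line.

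This is good evidence of intent, and it stands as such. It does not put the condition into the eligibility, FAS or index rules. The first-line stratum and first-line subgroup fix line, not stage, and the primary analysis is unchanged by any of these.

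A reader might infer that the control arm does contain patients selected for failing. The documents do not show that: no passage identifies a control who was local at first-line chemotherapy, and the stage list in Protocol 9.3.4 covers both arms. Nor is moving to advanced stage a failure in itself. The primary endpoint counts a new systemic therapy, radiotherapy, mutilating surgery or death, which would often follow but need not.

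**Conclusion.** The point holds as a gap in the rules. As written, they allow a control to enter through a post-index event and to be counted from before it. The selection would be confined to the control arm and would tend to favour larotrectinib.

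Its size is unknown and may be zero. The figures above rest on assumed numbers of affected controls and on pC = 0.19, a planning value taken from a published series and not this cohort's rate. In particular, a reader might conclude that the control failure rate would roughly halve. That takes 4 of the 8 failures being affected and either removed or never failing again; when affected controls are re-indexed and kept, no change at all is also within the range.

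A reader might also conclude that the primary estimate is biased towards larotrectinib overall. That is not established either. Most SCOUT patients are indexed at second line or later and controls at first line, which the plan expects to work against larotrectinib, and the documents give no means of weighing the two. What does follow is that the description of the primary estimate as leaning against larotrectinib cannot be relied on until this route is closed or shown to be empty. The exploratory status of the results limits the consequence but does not remove it, since the comparison is meant to inform a reimbursement reassessment.

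**What to change.** In SAP 5.1.1, 6.2.1 and 6.3.1 to 6.3.6:

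- Require locally advanced or metastatic disease to be documented on or before the index date, in both arms.
- Define the control index as the start of the first chemotherapy line begun on or after that date. This brings Protocol 9.3.1, 9.3.3 and 9.7.1 and SAP 6.2.1 and 6.3.6 into line with the abstract's PFS wording.
- Exclude controls with no such line.
- Report how many controls are re-indexed and how many are excluded. If both counts are zero, say so; the results then do not change.

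The cost is a few sentences and one derivation, using a date that Protocol 9.3.4 already lists for collection. The downside is that a few of the 42 controls may be re-indexed or lost, and the comparison may look less favourable to larotrectinib.
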